# Study population:

Any child who has not as yet received any of the vaccines scheduled at 6 week of age will be screened for participation in this study. All participants need to fulfill all inclusion and exclusion criteria, as detailed below, prior to randomization into the study.

Study inclusion criteria:

- 1. Signed informed consent by the parent/guardian of the child;
- 2. Born to an HIV-uninfected women, based on testing undertaken as part of standard of care during the last trimester of pregnancy;
- 3. Had not received any vaccine other than BCG and OPV (routinely given at birth) prior to enrolment;
- 4. Birth weight >2499g AND weight of child >3.5 kg at time of proposed randomization;
- 5. Aged 42-56 days of age at time of enrolment;
- 6. Available for the duration of the study;
- 7. Child is healthy based on medical history and physical examination of the study-staff.

Protocol: PCV1+1, version 2.116 Protocol date: 6th February 2017

#### Exclusion criteria:

- 1. Any clinically significant major congenital abnormalities;
- 2. Previous hospitalization for a respiratory illness following discharge from hospital after birth;
- 3. Receipt of any other investigational drug/vaccine. Co-enrollment into non-investigational studies, including epidemiology studies, is allowed;
- 4. Any previous PCV vaccination;
- 5. Known allergy to any of the vaccine components;
- Febrile illness (axillary temperature ≥37.8°C) at time of enrolment. These participants are eligible if the temperature resolves for at least 48 hours and they remain within the study defined window periods;
- 7. Planned relocation to outside of the study area during up until age of 2 years;
- 8. Receipt of blood transfusion or any other blood products (including immunoglobulins) since birth. Receipt of such products during the course of the study, will require withdrawal of the child from the study;
- 9. History of confirmed pneumococcal disease since birth;
- 10. Any known or suspected immunodeficiency condition which could affect immune response to vaccination.

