Endpoint 6.2: The percentage of participants in a subset achieving a serotype-specific OPA titer greater or equal to serotype-specific threshold proposed by Andrews et al. as a OPA correlate of protection against IPD for each of the pneumococcal serotypes measured 1 month after the 9-month booster dose for each 1+1 vaccine group compared to the 2+1 group of the same vaccine formulation.

 Compare the vaccine-serotype specific serum OPA geometric mean titers (GMT) one month following the booster dose of differing 1+1 dosing schedules compared to the immune response following a 2+1 dosing schedule on the subset in whom OPA are undertaken.

Endpoint: The lower limit of the 95% confidence interval of the ratio of OPA GMT one-month following the booster dose of PCV of the 1+1 and 2+1 dosing schedules being >0.5 for at least 10 of the PCV13 serotypes and eight of the PCV10 serotypes.

8.

To evaluate GMCs of serotype specific antibody concentrations at 18 months of age in the different 1+1 dosing arms compared to the 2+1 dosing group.

Endpoint: The lower limit of the 95% confidence interval of the ratio of GMC of the 1+1 and 2+1 dosing schedules being >0.5 for individual serotypes.

Colonization outcome:

9. To compare the prevalence of vaccine-serotype (stratified by PCV10 and PCV13 serotypes) and non-vaccine serotype nasopharyngeal colonization at 9, 15, and 18 months of age for the 1+1 dosing schedule groups compared to the 2+1 groups.

Endpoint: Prevalence of overall vaccine-serotype colonization and stratified by PCV10 and PCV13 serotypes at 9, 15 and 18 months of age in the 1+1 compared to 2+1 dosing arms, stratified for the individual PCV formulation.

Safety outcome:

10. The number of participants reporting adverse events in the 1+1 dosing groups and the 2+1 dosing groups throughout the study including specifically physician diagnosed all-cause

Protocol: PCV1+1, version 2.112 Protocol date: 6th February 2017 clinical pneumonia (and vaccine-serotype IPD), including out-patient or hospitalized episodes.

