This study will be undertaken in a setting where there are robust prevailing data on the incidence of IPD and prevalence of serotype specific colonization, including data from studies dating back to mid-1990s. Although PCV10 has three fewer serotypes included in it, there is supporting evidence to show cross-protection against serotype 6A and possibly serotype 19A (especially after a booster dose of vaccine), hence, effectively the vaccine coverage for PCV10 would be similar to that for PCV13, as serotype 3 (not included in PCV10) is relatively uncommon (<2% of invasive isolates prior to PCV immunisation) in South African children . Both PCV13 and PCV10 are licensed for use in South Africa.

Although the immunogenicity of the 2+1 dosing schedule of PCV10 and PCV13 per South African public immunisation program recommendation has been previously evaluated , we propose including such a dosing arm as a comparator group in the current study, since changes in circulation of the vaccine serotypes could theoretically influence the immune responses to even

Protocol: PCV1+1, version 2.114 Protocol date: 6th February 2017 this dosing schedule. Furthermore, considering the low incidence of PCV13-serotype IPD among HIV-unexposed children in South Africa in 2012 (1 per 10 000, which has likely declined even further since), it is unlikely that we would have any vaccine-serotype IPD cases among the study cohort of 600 participants against which to measure the relative efficacy of the different PCV formulations. In lieu of determining whether there is any likely clinical offset of a reduced dosing schedule, we propose to evaluate serotype specific pneumococcal colonization during the study. Although colonization is a pre-requisite to developing pneumococcal disease, the majority of pneumococcal colonizing events are asymptomatic, with the prevalence of PCV13 serotype colonization having decreased from 29% in 2010 to 14% in 2012, with further declines anticipated to have occurred since then (data from 2014/5 are currently being analyzed).

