# Safety monitoring

The study will undertake passive surveillance for hospitalizations of study participants, including for pneumonia and invasive pneumococcal disease, throughout the study. A Data and Safety Monitoring Board (DSMB) will be established to review whether any of the hospitalizations are possibly due to pneumococcal disease (with a specific focus on IPD and radiologically confirmed pneumonia) and determine whether there is any trend to an excess of cases in any of the 1+1 dosing arms compared to the 2+1 dosing arm. Summary reports of all hospitalizations, radiologically confirmed pneumonia and IPD (including serotype data) will be provided to the DSMB on a quarterly basis, and more frequently if requested. The incidence (per 100,000) of PCV13 vaccine-serotype IPD among HIV-unexposed children in 2012 in Soweto was 20.6, 0, 5.6 and 0 in age groups <10 weeks, 10 wks to 6 months, 6.1-12 months and 9-12 months of age, respectively. As such no cases would be expected in a sample size of 600 participants, a hold on further enrolment into the study will, however, be implemented if there are more than three cases of PCV13 serotype IPD across any of the 1+1 dosing schedules if occurring at least 4 weeks after receipt of the first dose of PCV in that group. The DSMB will determine whether the study should then be discontinued. If the study is discontinued all the children in the 1+1 dosing arms will default to a 2+1 dosing schedule if age appropriate or receive another dose of PCV as required. The DSMB will also be tasked with evaluating the post-booster data from the study, to determine whether the children in any of the 1+1 dosing arm should be offered an additional dose of PCV in the presence of significant inferior immune responses to the PCV schedule

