## Criteria for Study Discontinuation

The participant's parent/legal guardian refuses further treatment and/or follow-up evaluations. The investigator determines that further participation would be detrimental to the participant's health or well-being.

The participant's parent/guardian fails to comply with the study requirements so as to cause harm to him/ her or seriously interfere with the validity of the study results.

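### Exclusion criterion 8 withdraws a child given a blood product after randomisation from the whole study, so later safety events and swabs still due are lost when only the antibody data need protecting

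*Protocol*

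**What the plan says.** The protocol's Exclusion criteria, item 8, opens as an ordinary entry criterion: "Receipt of blood transfusion or any other blood products (including immunoglobulins) since birth". It then reaches past randomisation: "Receipt of such products during the course of the study, will require withdrawal of the child from the study". The rule is compulsory, and its object is the study, not the blood sampling or the antibody analysis.

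The safety and colonisation objectives are framed as follows.

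- Secondary objective 10 counts "The number of participants reporting adverse events in the 1+1 dosing groups and the 2+1 dosing groups throughout the study", with physician-diagnosed pneumonia and vaccine-serotype IPD named specifically.
- Safety monitoring: "The study will undertake passive surveillance for hospitalizations of study participants, including for pneumonia and invasive pneumococcal disease, throughout the study". Quarterly summaries go to the DSMB, which compares the 1+1 arms with 2+1.
- Secondary objective 9 compares "nasopharyngeal colonization at 9, 15, and 18 months of age for the 1+1 dosing schedule groups" with the 2+1 groups. Because too few IPD cases are expected to compare arms, Study Design makes colonisation the stand-in for any clinical cost of fewer doses: "we propose to evaluate serotype specific pneumococcal colonization during the study".

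Criteria for Study Discontinuation gives three reasons. The first is "The participant's parent/legal guardian refuses further treatment and/or follow-up evaluations"; the others are investigator judgement of detriment and parental non-compliance. Blood products are not among them. The ethics section describes referral for vaccination after consent is withdrawn, but no off-study follow-up.

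**The concern.** The protocol gives no reason for the rule. The obvious one is that donor antibody, or its effect on later vaccine responses, could distort the serotype-specific IgG results. That concerns the antibody endpoints. It is no reason to stop recording hospitalisation, pneumonia or IPD, or to stop taking swabs.

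The trigger is a medical event after randomisation, so the children who leave cannot be treated as a random sample of their arm. An analysis plan can leave out an affected serum, but it cannot recover follow-up that was never collected. The question therefore has to be settled in the protocol, whatever the statistical analysis plan says. In addition, a site that looks for withdrawal rules under the discontinuation heading will not find this one.

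**Working it through.** **1. The sections side by side.** Item 8 ends participation. Objective 10 and Safety monitoring describe follow-up of participants for the length of the study. No section limits item 8 to sera, and none provides for safety or swab follow-up afterwards.

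**2. What is kept and what is lost.** The illness that led to the product comes before withdrawal. It is captured by the recording of all Grade 2 or higher events (Toxicity Management), the 24-hour reporting of death and IPD (SAE Reporting Requirements) and the quarterly hospitalisation reports. Lost are later events and later swabs:

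- withdrawn before 9 months: 3 swabs
- between 9 and 15 months: 2 swabs
- between 15 and 18 months: 1 swab

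These ages come from objective 9 and the visit schedule. The laboratory section on swabs gives 9, 12 and 18 months, a separate inconsistency.

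**3. How many children.** The protocol gives no rate. Assume 0.5% to 3%: 600 × 0.005 = 3 and 600 × 0.03 = 18 children, or 0.5 to 3 per arm of 100.

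**4. Primary comparison.** Inputs from the sample size section and Table 1: margin ratio 0.5, so log10(2) = 0.301; adverse difference 0.05 log10 (the 1.12 row); SD 0.4; one-sided alpha 0.02; n = 91.

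- Noncentrality = (0.301 − 0.05) / (0.4 × √(2/91)) = 0.251 / 0.0593 = 4.23. The noncentral t gives power 0.9844, which reproduces the tabulated 0.984.
- Suppose the blood-product losses come on top of the planned losses. At n = 91 − 0.5 = 90.5, power is 0.9839. At n = 91 − 3 = 88, it is 0.9814.

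**5. Later safety events missed.** Let s be the share withdrawn and R their assumed event risk relative to the other children over the period after withdrawal. The share of events in that period that goes unobserved is sR / (sR + 1 − s).

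| s | R = 2 | R = 10 |
|---|---|---|
| 0.5% | 1.0% | 4.8% |
| 1% | 2.0% | 9.2% |
| 3% | 5.8% | 23.6% |

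Both s and R are assumptions.

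**6. Vaccine-serotype IPD missed.** Safety monitoring gives 2012 rates of 20.6 per 100,000 (under 10 weeks) and 5.6 per 100,000 (6.1 to 12 months), treated here as annual. Assume withdrawal at 4 months, so 18 − 4 = 14 months are lost.

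- High, 12 children (2%), tenfold risk: 12 × 0.000206 × 10 × 14/12 = 0.029 cases.
- High, 18 children (3%), tenfold risk: 18 × 0.000206 × 10 × 14/12 = 0.043 cases.
- Low, 3 children, no excess risk: 3 × 0.000056 × 14/12 = 0.0002 cases.

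**The case against.** The best defence is that there is no strict contradiction. Any withdrawal rule limits follow-up of participants, and the three listed discontinuation criteria do so as well. That list does not claim to be complete, and nothing in it tells a site to keep a transfused child. This stands: the sections fit together poorly, but they do not give opposite instructions. It leaves open why this particular loss is needed.

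A second point is that numbers are probably small. Entry is restricted to healthy infants with birth weight above 2499 g and without major congenital abnormality or suspected immunodeficiency, and the sample size already carries a 10% allowance for loss and early withdrawal. This also stands, and it limits the severity.

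A third point concerns the remedy. The background section says maternally acquired antibody could dampen the response to a first PCV dose. By the same reasoning, a product given before a dose might alter the response to that dose after the donor antibody has gone. Dropping only sera drawn within a short interval may therefore not be enough. This stands, and the fix allows for it.

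A reader might infer that the rule removes the sickest children and so hides harm in the reduced-schedule arms. The documents do not support that. They do not say who receives blood products, the rule also covers immunoglobulins given for any reason, and the illness that prompts the product is recorded and reaches the DSMB. An IPD case that led to a transfusion could still count towards the enrolment-hold rule.

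**Conclusion.** The point holds as a cheap improvement of minor to moderate severity. A compulsory withdrawal triggered by a medical event ends safety and swab collection that the trial has otherwise planned, and the only evident reason for it concerns antibody results.

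The effect on the primary GMC comparison is negligible: per-serotype power is no lower than 0.981 against 0.984 over the assumed 0.5% to 3%. The effect on later safety events cannot be quantified from the protocol. The assumed values span about 1% to 24% of events in the period after withdrawal, and the upper end needs both 3% withdrawn and tenfold risk.

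A reader might also infer that one unobserved IPD case is likely and would change the safety conclusion, since almost none are expected. On the protocol's own rates, the expected number missed is about 0.03 to 0.04 even with tenfold risk. Nor is colonisation follow-up cut short continuously: it consists of three fixed swabs, and only those still due are lost.

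**What to change.** Reconcile Exclusion criterion 8, Criteria for Study Discontinuation, objective 10 and Safety monitoring, so that they state together:

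- Receipt of a blood product after randomisation affects only which sera enter the immunogenicity analyses.
- The rule for those sera is fixed before laboratory results are unblinded. It covers sera drawn after the product, including responses to PCV doses given after it, and does not assume that a short interval is enough.
- Safety surveillance and the scheduled nasopharyngeal swabs continue with parental consent.

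Whether such a child receives further study vaccine is a clinical matter for the sponsor and is not prescribed here.

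The cost is a short amendment, a CRF flag with the date and type of product, and a few sera to identify and exclude. No visit or sample is added to those already planned.

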### Study procedures:

#### Study population

The study will be undertaken in Soweto, South Africa. Parents of prospective study participant will be identified at the time of birth at Chris Hani-Baragwanath Academic Hospital (CHBAH) or at one of the neighboring primary health care clinics, including midwife operated units and the immunisation clinics at these facilities prior to receiving their vaccine at 6 weeks of age.

#### Study randomization

Participants consented for study-participation will be randomized into one of 6 study arms in a 1:1:1:1:1 ratio. The six groups will include children randomized to either one of the two 1+1 dosing schedules (1st dose given at either 6 or 14 weeks of age) and the 2+1 dosing group (per current South African public immunisation schedule at 6 weeks, 14 weeks and 9 months of age), using either PCV10 or PCV13. The booster dose in all study groups will be given at 9 months of age. Participants eligible for enrolment will be allocated a sequential study number and randomization undertaken manually with allocation to study group for specific study-numbers having been generated by the study statistician using blocks of 30.

Protocol: PCV1+1, version 2.117 Protocol date: 6th February 2017

### Study vaccine

Both study-vaccines, i.e. PCV10 (Synflorix®) and PCV13 (Prevnar-13®), are currently licensed in South Africa.

PCV13 (Prevnar-13®) contains saccharides from pneumococcal serotypes 1, 3, 4, 5, 6A, 6B, 7F, 9V, 14, 18C, 19A, 19F and 23F individually conjugated to nontoxic diphtheria toxin cross-reactive material 197 (CRM197). The vaccine is formulated to contain 2.2 µg of each saccharide, except for 4.4µg of 6B, per 0.5-mL dose. The vaccine is formulated with 5 mM succinate buffer, 0.02% polysorbate 80, and 0.125 mg of aluminum as aluminum phosphate, per 0.5-mL dose.

PCV10 (Synflorix®) consists of 1 µg capsular polysaccharide for serotypes 1, 5, 6B, 7F, 9V, 14, and 23F, and 3 µg for serotype 4, each individually conjugated to protein D of non-typeable H. influenzae, and 3 µg of capsular polysaccharide of serotypes 18C and 19F conjugated to tetanus and diphtheria toxoids, respectively. The PCV vaccines will be procured commercially. Study vaccines will be administered by qualified medical staff, with PCV being administered intramuscularly by injecting 0.5 mL into the anterolateral thigh muscle of the left leg at the vaccination visits, with the details (i.e., date of administration, randomization number, site of administration) recorded on the case report forms (CRF).

In addition, children will receive the other vaccines included in the public immunisation program (including Hexaxim®, measles and rotavirus vaccine) per recommended public immunisation schedule. All routinely administered injectable vaccines given concurrently with PCV will be administered in a limb other than where the PCV vaccine was given. All the routinely administered vaccines included in the public immunisation program will be sourced through the immunisation program by RMPRU, which is an accredited immunisation facility of the Department of Health. The dosing schedules for the PCV Groups and the other routinely administered vaccines are shown in Table 2. As a benefit to the children, all participants will be assigned to receive either a single dose of Hepatitis A vaccine or varicella vaccine at 15 months of age, both of which are registered in South Africa, but neither of which are included in the public immunisation rough and in the public immunisation program. Allocation to varicella or Hepatitis A vaccine will be based on whether the child's study randomization number ends in an even (Hepatitis A vaccine) or odd number (Varicella vaccine). In the event of unavailability of either of these vaccines during the study, the alternate vaccine will be provided to the child.

The PCV and other vaccines will be stored at 2-8°C in a temperature- monitored refrigerator at the RMPRU pharmacy, with control of vaccine stock undertaken by the site-pharmacist. The refrigerator is secure with limited access and temperature monitoring is undertaken on a 24/7

Protocol: PCV1+1, version 2.118 Protocol date: 6th February 2017 automated system, with alerts being sent to the pharmacist and other study staff in the event of excursions outside of the defined range.

### Trial visit details

#### Visit 1 (6 weeks of age, day 42-56 of life):

For all participants, informed consent will be signed, inclusion and exclusion criteria reviewed, medical history will be collected and physical examination (including weight and length measurements) and randomization will be performed.

Blood draw for testing of baseline antibody concentrations against vaccine preventable diseases All participants will receive Hexaxim® and Rotavirus vaccine as per EPI.

Group 1 & 3 participants will also receive PCV10/ PCV13 (as per randomisation).

All participants will receive a visit appointment card, and the next visit will be scheduled.

#### Visit 2 (10 weeks of age; 28-35 days post visit 1):

All participants will have a physical examination (including weight and length measurements) and will receive Hexaxim® vaccine as per EPI.

Group 1 participants will have a blood draw for ELISA for PCV vaccine serotypes (28-35 days post vaccine administration).

All participants: next visit will be scheduled.

## Visit 3 (14 weeks of age; 28-35 days post visit 2):

All participants will have a physical examination (including weight and length measurements) and will receive Hexaxim® and Rotavirus vaccine as per EPI.

Group 2 & 3 participants will also receive PCV10/ PCV13 (as per randomisation).

All participants: next visit will be scheduled.

## Visit 4 (18 weeks of age; 28-35 days post visit 3):

All participants will have a physical examination (including weight and length measurements). Group 2 & 3 participants will have a blood draw for ELISA for vaccine serotypes (28-35 days post vaccine administration).

All participants: next visit will be scheduled.

Visit 5 (6 months of age; day 180 ±14 days):

All participants will have a physical examination (including weight and length measurements) and

will receive measles vaccine as per EPI. Protocol: PCV1+1, version 2.119 Protocol date: 6th February 2017 All participants: next visit will be scheduled.

## Visit 6 (9 months of age; day 270 ±14):

All participants will have a physical examination (including weight and length measurements) and will receive PCV10/ PCV13 (as per randomisation).

A nasopharyngeal swab will be taken from all participants prior to vaccine administration for culture/ PCR detection of PCR serotypes.

All participants will have a blood draw for draw for ELISA for vaccine serotypes All participants: next visit will be scheduled.

# Visit 7 (10 months of age; 28-35 days post visit 6):

All participants will have a physical examination (including weight and length measurements). All participants will have a blood draw for ELISA for PCV vaccine serotypes AND PCV OPA and vaccine preventable diseases (28-35 days post vaccine administration). All participants: next visit will be scheduled.

